1. OBJECTIVE(S) AND ENDPOINT(S)

1.1. **Objective**(s)

• To evaluate the benefit of topical applications of sunflower seed oil (SSO) to children aged 2-24 months with SAM

1.2. Endpoint(s)

This is an exploratory open-label study to evaluate potential benefits of topical application of (SSO in SAM. There is little or no historical data available on efficacy endpoints, therefore an interim analysis was planned when 100 evaluable subjects have completed the study. The results from the interim analysis will help identify key/primary efficacy endpoints. Therefore, the list of endpoints and analysis plan may be updated after the interim analysis.

The endpoints which will be investigated in the analysis are:

Primary Endpoints

• Weight gain (g/kg/day)

Secondary Endpoints

- Time (days) to discharge from acute phase
- Rate of suspected nosocomial infections (nosocomial infection will be diagnosed clinically as per hospital's management guidelines where it has been mentioned that any new sign of infection during hospital stay that was not present at admission will be considered as nosocomial infection. Following the interim analysis, the list of nosocomial infections was restricted to pneumonia, fever, UTI and sepsis.)
- Change from baseline in transepidermal water loss (TEWL) at Day 10
- Change from baseline in plasma fatty acid levels at Day 10*
- Change from baseline in c-reactive protein (CRP) at Day 10
- Change from baseline in pro-inflammatory cytokine parameters at Day 10

- Clinical improvement of visual skin condition:
 - Change from baseline in skin redness at Day 10
 - \circ Change from baseline in skin condition score at Day 10
- Change from baseline in the skin and gut microbiome data at Day 10*
- * Change from baseline in plasma fatty acid levels at day 10 will not be included in the interim analysis as the results will not be available until the end of the study. The analysis of plasma fatty acid levels will be included in the final study report. However, this analysis is outside the scope of this RAP.
- * Change in the skin and gut microbiome data will be collected for a sub-sample of subjects in the study as described in the protocol amendment. This analysis will be performed at the end of the study by an external expert at Stanford University. The metabolomic data will be analysed by the CRO (Metabolon) and additional support will be provided by the GSK subsidiary company Cellzome. As previously indicated, the analysis of skin and gut microbiome data is outside the scope of this RAP.

2. STUDY DESIGN

Please refer to the protocol for details on the study design and sample size.

3. PLANNED ANALYSES

An interim analysis was planned when approximately 100 evaluable subjects have completed the study. For further details of the planned interim analysis, refer to the RAP version 1 dated 09-Jun-2016.

A final analysis will be conducted when all subjects have completed the study and all data have been entered, checked and cleaned.

4. ANALYSIS POPULATIONS

The following populations will be defined:

Safety population: The safety population will comprise all randomised subjects who start the SAM Routine Standard of care (with or without topical application of SSO) and will be used for the analysis of safety data. The data will be analysed according to the actual treatment received if this differs from the treatment to which the subject was randomised. If subjects receive treatment differing from that assigned by the randomisation schedule (for either a portion of or the entire time on study), they will be

analysed based on the treatment taken for the majority (>50%) of their time on study treatment.

Intent-to-Treat (ITT) population: This will consist of all randomised subjects from whom at least baseline and at least one post baseline measure have been obtained and will be used for the analysis of efficacy data. The data will be analysed according to the treatment to which the subject was randomised.

5. TREATMENT COMPARISONS

5.1. Data Display Treatment and Other Sub-group Descriptors

The descriptors as detailed below will be used to denote the study treatment and will be used in the data displays:

- Emollient Therapy
- No Emollient

6. GENERAL CONSIDERATIONS FOR DATA ANALYSES

All programming will be performed using - SAS (version 9.4 or later), SPSS or STATA. The analysis will be carried out in collaboration with icddr,b, and Stanford University. Further analysis of the SCORDoK score may be carried out by the Denmark SCORDoK team. The metabolomic data will be analyzed by the CRO assaying the samples (Metabolon) with input from representatives from the R&D Platform Technology & Science group within the GSK subsidiary company Cellzome All analyses will be deemed exploratory.

6.1. Strata and Covariates

Randomisation was planned to be stratified by age at baseline in two strata: 2-<6 months and 6-24 months in a 1:2 ratio. However, as noted in the amended protocol, additional subjects may be enrolled in the older subgroup.

The two age group strata (2-<6 months and 6-24 months) will be the categories used in all tables, figures and listings split by age group unless stated otherwise.

The statistical analysis will be adjusted for age at baseline (as a continuous covariate), sex and a measure of the parameter or severity at baseline as specified in the table below. In addition, the analysis of weight gain will include average calorie intake divided by baseline weight (calorie intake per day per kg).

Patients will be categorised as "Oedematous" if they are recorded on the CRF as having oedema at any time during the study. Otherwise they will be categorised as "Non-oedematous". For each patient, the daily calorie intake (total energy per day) is collected on the CRF. The average of these values divided by baseline weight will be used as the calorie intake covariate.

If an inadequate number of subjects is observed in one of the categories for sex or oedematous status then the covariates may be removed from the models.

In addition to the above, differences between the two treatment groups (emollient therapy versus no emollient) will be examined with respect to baseline characteristics prior to performing statistical analysis of the efficacy endpoints. If any differences are considered to be clinically important, exploratory subgroup analysis may be presented for the relevant endpoints.

Depending on the method of statistical analysis, covariates/factors specified below will be fitted in each model. If any terms are not significant then they may be dropped from the final analysis.

Method of analysis	Endpoints]	Fixed effects te	erms	Random effects terms
		Continuous Covariates	Factors	Interactions	Covariates
ANCOVA	Fatty Acids	Baseline of parameter, age	Treatment, sex		
MMRM	Weight	Baseline of parameter,	Treatment, day, sex,	Baseline of parameter	Subject (in the subject
	TEWL	age, calorie intake per	oedematous status	*day, treatment*day,	option of the repeated
	Skin redness	day per kg ^[2] , mean breast		treatment*age category, treatment*age	statement in proc mixed)
	Skin Appearance	feeding frequency ^[2]		category*day ^[3]	
Cox	Discharge	Baseline	Treatment,		
proportional	from acute	weight-for-	sex		
hazard	phase	length Z			
model		score, age			

Table 1: Covariates/Factors to be included in statistical analyses

Logistic	Suspected	Baseline	Treatment,	
regression	nosocomial	weight-for-	sex	
	infections	length Z		
		score, age		

- [1] Oedematous status and calorie intake was only to be included in the analysis of weight at interim. After interim, since there were only 4 subjects with oedema, the decision was taken to remove subjects with oedema from the statistical analysis. Oedematous status was therefore removed as a covariate.
- [2] Based on further information from the data and from site the decision was taken to adjust for calorie intake per day per kg rather than calorie intake. Also, it was decided to use mean breast feeding frequency as a covariate for the weight analysis only
- [3] The additional interactions of treatment*age category and treatment*age category*day was included after the review of interim analysis results to investigate the differences in endpoints between the two age categories. Note, the age categories are: 2-<6 months and 6-24 months.
- [4] Note, the statistical analysis of endpoints related to the skin and gut microbiome data is not included here, because this analysis will be performed by experts in the field at Stanford University, California, USA. Also, the analysis of the metabolomic data will be performed by a CRO Metabolon with additional input from representatives of the GSK subsidiary company Cellzome.

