9.2. Time (days) to discharge from acute phase

Derivations

Discharge from the acute phase is based on improvement in mental state, normalisation of vital signs, re-establishment of oral feeding and resolution of all acute illnesses.

The CRF collects information on whether a patient is ready for discharge from the acute phase (Y/N) daily. Time (days) will be derived as the number of days between baseline and the first occurrence where 'Ready for discharge from acute phase' was recorded as Yes. Baseline will be taken as the earliest measurement recorded in the daily monitoring chart. Day will be derived relative to the baseline.

If a subject withdrew or died before being ready for discharge from the acute phase then they will be censored at the time they left the study. Patients who completed Day 10 before being ready for discharge will be followed up by the site until they withdraw or are ready for discharge.

Kaplan Meier

A Kaplan-Meier plot including 95% CIs and the number of subjects at risk at each day will be presented.

Cox Proportional Hazards

The time to discharge from acute phase will be compared between treatment groups using a Cox's Proportional Hazards model adjusting for the covariates specified in Section 7.1.

The time to discharge from acute phase will be presented in quartiles for each group. The hazard ratio, 95% CI and associated p-value will also be presented.

Residual plots from the Cox proportional hazard model and the Kaplan-Meier plot will be used to visually check the assumption of proportional hazards is fair. If the proportional hazard assumption is invalid, then other methods of analysis may be considered which do not make this assumption, for example a Weibull model may be fitted to the data.

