9.3. Rate of suspected nosocomial infections

Derivations

Any new sign of infection during hospital stay that was not present at admission or not present for last 48 hours of hospital stay will be considered as nosocomial infection. Occurrence of the following four suspected nosocomial infections, pneumonia, fever, UTI and sepsis, is collected on the CRF. Subjects will be considered as having had a suspected nosocomial infection if they have at least one of these four infections where symptoms started during the 10-day treatment period. Pneumonia, fever, UTI and sepsis were identified during the interim results meeting as the key nosocomial infections of interest.

Summary Statistics

The number and percentage of subjects who have at least one suspected nosocomial infection during the 10 day treatment period will be summarised by treatment group. In addition the total number of infections (1, 2, 3, >3) and the type of infection will be summarised as frequency counts and percentages.

Following the interim analysis, nosocomial infections will also be summarised by age category.

Logistic Regression

The proportion of subjects who have at least one suspected nosocomial infection in each treatment group will be compared using a logistic regression. Covariates/ factors will be included in the model as described in Section 7.1Error! Reference source not found.. The odds ratio with associated 95% CI will be presented.

This analysis may not be performed if there are a low number of suspected nosocomial infections.

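### The Cox and logistic models adjust for continuous age but not for the age group used to stratify randomisation; this is minor, but it can cost the Cox comparison power if discharge changes sharply at 6 months

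*SAP*

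**What the plan says.** - **Design.** SAP section 6.1: "Randomisation was planned to be stratified by age at baseline in two strata", namely 2-<6 and 6-24 months, at 1:2. The split may shift, because "additional subjects may be enrolled in the older subgroup". Section 9.1 describes age category as based on the randomised strata.
- **Form of age.** Section 6.1: "The statistical analysis will be adjusted for age at baseline (as a continuous covariate), sex", plus a baseline measure of the parameter or of severity.
- **Table 1, Cox and logistic rows.** The continuous covariates are baseline weight-for-length Z score and age; the factors are treatment and sex. Neither row lists an age category, a stratum, an interaction or a non-linear age term.
- **Model text.** Section 9.2: time to discharge is "compared between treatment groups using a Cox's Proportional Hazards model adjusting for the covariates specified in Section 7.1". Section 9.3: "The proportion of subjects who have at least one suspected nosocomial infection in each treatment group will be compared using a logistic regression", with covariates from the same place. Section 7.1 is in fact the baseline definition, so both references are read here as meaning Table 1 in section 6.1.
- **Where age group is used.** Table 1 has it as interactions in the repeated-measures row. Its note 3 says these were added after the interim review to look at differences between the age categories. Section 9.3 adds a descriptive summary of infections by age category. Section 9.2 does not use age group.
- **Dropping rule.** Section 6.1 allows any term that is not significant to be left out of the final analysis. Age is not protected.
- **Status.** Both endpoints are secondary (section 1.2). All analyses are exploratory (section 6), with no multiplicity adjustment (section 6.2).

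**The concern.** A factor used to stratify randomisation normally appears in the analysis. Here its role is left to one age term, which has to be read as linear because no other form is given. A straight line over 2 to 24 months cannot reproduce a step at 6 months. Any step that remains is unexplained prognostic variation. In Cox and logistic models such variation tends to pull the hazard or odds ratio towards 1 and to reduce power. The dropping rule could then remove age altogether.

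At stake is some power, mainly for time to discharge. The validity of the tests is not at stake.

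**Working it through.** **No plan figure to reproduce.** The SAP gives no sample size, event rate or power for either endpoint; section 2 refers to the protocol for sample size. The check is therefore a simulation on assumed inputs.

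**Inputs from the SAP:** two age strata in a 1:2 ratio, and the terms of the two models.

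**Assumed inputs:**
- N = 200, with 1:1 allocation balanced within strata.
- Age uniform within stratum (2 to 6, and 6 to just under 25 months).
- Treatment log odds ratio -0.8 (odds ratio e^-0.8 = 0.45), with logistic intercept -0.4.
- Treatment log hazard ratio 0.48 (hazard ratio e^0.48 = 1.62), with baseline hazard 0.2 per day and censoring at day 20.
- Two-sided 5% Wald tests, 1,500 trials per setting.

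**Step 1: how much of the stratum does continuous age already carry?** The mean ages are 4 and 15.495 months.
- Between-stratum variance: (1/3)(2/3)(11.495²) = 29.36.
- Within-stratum variance: (1/3)(4²/12) + (2/3)(18.99²/12) = 0.44 + 20.03 = 20.48.
- R² = 29.36 / (29.36 + 20.48) = 0.59, a correlation of -0.77 with the indicator for the younger group.

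The age term therefore already does much of the work.

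**Step 2: power of the SAP model (continuous age) against age plus age group.**

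| True age effect | Logistic: SAP | Logistic: + age group | Cox: SAP | Cox: + age group |
|---|---|---|---|---|
| None | 74.5% | 74.4% | 90.4% | 90.3% |
| Linear, -0.1 per month | 67.2% | 67.2% | 91.4% | 91.1% |
| Step of 1.0 at 6 months | 70.9% | 71.9% | 85.5% | 90.1% |
| Step of 2.0 at 6 months | 59.9% | 63.7% | 77.4% | 89.5% |

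Steps are on the log-odds or log-hazard scale: 1.0 is a ratio of e^1.0 = 2.7 between age groups, and 2.0 is a ratio of e^2.0 = 7.4.
- Gain for Cox: 90.1 - 85.5 = 4.6 points, and 89.5 - 77.4 = 12.1 points.
- Gain for logistic: 71.9 - 70.9 = 1.0 point, and 63.7 - 59.9 = 3.8 points.
- Largest cost when the extra term is not needed: 91.4 - 91.1 = 0.3 points.

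The Monte Carlo standard error of one power figure is about √(0.7 × 0.3 / 1500) = 1.2 points at 70% and √(0.9 × 0.1 / 1500) = 0.8 points at 90%. The 1.0-point logistic difference is of that order. All models were fitted to the same simulated trials.

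**Step 3: validity.** With no treatment effect, the SAP models rejected in 4.7-5.6% of trials across all settings and both endpoints.

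**Step 4: a stratified Cox fit.** Step 2 entered age group as a covariate. A smaller simulation compared continuous age alone with a Cox model stratified by age group. It used 400 trials per setting, N = 200, true log hazard ratio 0.405, times rounded up to whole days and Efron ties.

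| Step (log hazard) | Estimate: age only | Estimate: stratified | Power: age only | Power: stratified |
|---|---|---|---|---|
| 1.0 | 0.393 | 0.421 | 75% | 80% |
| 1.5 | 0.351 | 0.398 | 65% | 73% |

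At a step of 0.5 there was no material difference. At 1.0 the power gain is again about 5 points, but the estimates show no useful difference in bias: 0.393 is 0.012 below the truth and 0.421 is 0.016 above it. Attenuation is clear only at 1.5, where 0.351 is 0.054 below the truth.

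**Step 5: if age is removed.** In the step settings, the models with no age term were conservative (type I error 1.7-4.1%) and had the lowest power: Cox 82.9% at a step of 1.0 and 71.5% at 2.0. These runs left age out in every trial and did not imitate a significance-based drop.

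**The case against.** The strongest reply is that age, the variable behind the stratification, is adjusted for, and in finer form than the age group. If the effect is linear, continuous age clearly beats the age group alone (Cox power 91.4% against 83.3%). Type I error holds. A material loss needs a sharp break at 6 months over and above a trend, and the SAP offers no evidence of one. All of this stands.

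A reader might go further and infer that the plan weakens both comparisons, or that either is invalid. The document does not support that. The loss is conditional on the shape of the age effect, and for the logistic model it is about 1 point unless the age groups differ by an odds ratio of around 7.

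Nor do the repeated-measures models show an inconsistency. Note 3 to Table 1 gives their age-category interactions a subgroup purpose, not the purpose of reflecting the stratified design. Proportional hazards is not a ground either, since section 9.2 already plans checks and alternatives. No effect of enlarging the older stratum has been calculated.

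The dropping rule also has less force than it may seem to have. A strong age effect would usually be significant and so be kept, which makes the no-age figures an outer bound.

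Three things survive the reply. Randomisation age group is absent from both models. Its only proxy is unprotected. Adding age group while keeping continuous age costs next to nothing, so the argument that continuous age beats age group alone does not count against doing so.

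**Conclusion.** The point holds as a minor one. Both models omit the randomisation age group, rely on continuous age, and allow that term to be dropped. Neither test is invalidated.

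The size depends on the unknown age effect:
- **Linear or absent:** differences of 0.3 points of power or less.
- **Step of 1.0 at 6 months:** about 5 points for Cox and about 1 for logistic.
- **Step of 2.0 at 6 months:** about 12 points for Cox and about 4 for logistic.

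These figures rest on an assumed N of 200, a 1:2 age split with uniform ages, and assumed treatment effects and event rates. The step sizes are illustrations, not estimates from the trial. Both endpoints are secondary and exploratory, which limits the weight of the point further.

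**What to change.** In Table 1 and sections 9.2 and 9.3:
- Stratify the Cox model by randomisation age group (2-<6, 6-24 months).
- Add age group as a factor in the logistic model when there are enough infections to support it. Section 9.3 already allows for not fitting the model when infections are few.
- Keep continuous age in both models.
- Exempt age group from the rule on dropping non-significant terms.
- Correct the reference to Section 7.1 so that it points to section 6.1.

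The cost is about one line of code per model and a short edit to the text. Age group is already derived for the repeated-measures models, so no new data are needed. If the age effect proves linear or absent, the simulated cost of adding age group as a covariate was at most 0.3 points of power. The stratified Cox form was not run under exactly those two conditions, but it showed no material difference from the age-only model at a step of 0.5.

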9.1. Weight

Derivations

Weight is collected once every day (approximately at 9 am) and recorded on 'daily monitoring chart' for all participants. However, for intervention group only, weight is measured three times daily (approximately at 9 am, 5 pm and 11 pm) and recorded on 'Emollient application record' to measure the intervention material. The summaries and analysis of weight gain will be based on the daily 9AM measurements on 'Daily monitoring chart' only, however, all measurements will be considered in the derivation of baseline weight. Data from baseline up to and including day 10 (labelled as Day 1 to Day 11 on the daily monitoring chart CRF) will be included in the weight analysis as per the specification on the eCRF. At the time of interim and post interim, a footnote will be included to indicate this.

Weight measurements that were collected while a subject had detectable oedema will be excluded from the summaries and analysis. The earliest measurement in the daily monitoring chart where oedema status was recorded as 1 (no oedema) will be taken as the baseline weight. Following review of the interim analysis results, it was decided that all subjects with oedema would be excluded from the weight analysis only. Subjects with oedema would be summarised separately in the final clinical study report.

Weight will be summarised as a rate of weight gain (g/kg/day), as defined below:

Change from Baseline in Weight at Day X (g)	=	Weight at Day X (g) – Weight at Baseline (g)
Relative Change from Baseline	=	Change from Baseline in Weight at Day X (g)

in Weight at Day X (g/kg)

Weight at Baseline (kg)

Rate of Weight Gain at Day X (g/kg/day) Relative Change in Weight at Day X (g/kg)

Note: 'X' refers to the study day label (see Table 2, page 10) and not the day reported on the daily monitoring chart

Summary Statistics

The following endpoints will be summarised by day (day 0 - day 10), presenting the number of subjects, mean (with standard deviation) and median, minimum and maximum for each treatment group. The summaries for change from baseline, relative change from baseline and rate of weight gain will also present summary statistics for the last day the subject was in the study.

- Weight (kg)
- Weight (kg) by oedematous status
- Change from baseline in weight (g)
- Change from baseline in weight (g) by oedematous status
- Relative change from baseline in weight (g/kg)
- Relative change from baseline in weight (g/kg) by oedematous status

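### The primary weight model drops a child if oedema is recorded on any study day, so who is analysed depends on post-randomisation records

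*SAP*

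**What the plan says.** Section 6.1 puts a child in the oedematous category "if they are recorded on the CRF as having oedema at any time during the study", and everyone else in the non-oedematous category. Records made after Day 0 therefore count.

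Footnote [1] of Table 1 reports what followed the interim: "since there were only 4 subjects with oedema, the decision was taken to remove subjects with oedema from the statistical analysis". It then says that oedematous status was removed as a covariate for that reason. Section 9.1 (Derivations) gives the same decision with a narrower scope: "it was decided that all subjects with oedema would be excluded from the weight analysis only". The removed children are to be summarised separately in the study report. Sections 9.4 to 9.6 keep them in the analyses of water loss, redness and skin score.

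Just before this, Section 9.1 still carries a different rule that works weight by weight. It leaves out weights taken while oedema was detectable and uses the first oedema-free weight as baseline.

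Section 4 defines the ITT population without reference to oedema. Section 9 uses that population for efficacy unless something else is specified. Section 8.3 shows that presence of oedema at Day 0 is collected.

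**The concern.** Randomisation protects a comparison between groups formed at entry. Under the any-time definition, membership of the primary weight model is settled by what is recorded during the ten treatment days. Oedema that begins in that period may depend on treatment or on clinical course, and it acts directly on the outcome because fluid changes measured weight. Section 1.2 says "This is an exploratory open-label study", so a difference between arms in how oedema is recorded cannot be ruled out either.

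Two things are at stake. The treatment difference in weight gain can be biased if late-onset oedema, or the weight gain of children who develop it, differs between arms. In any case, oedema-free weights are discarded. The plan contains no weight model that would show whether the estimate is sensitive to this choice: the supplementary analysis in Section 6.3 concerns withdrawn children, and a separate descriptive summary of a few oedematous children cannot answer the question.

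**Working it through.** The SAP gives no figure for the effect of this rule, so there is nothing to reproduce. The check has two parts.

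**Tracing the rule**

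1. The exclusion sentences in footnote [1] and Section 9.1 speak of children with oedema and do not repeat the any-time wording.
2. Footnote [1] removes these children and, for that reason, the oedematous-status covariate. That covariate is the Section 6.1 variable, and the SAP has no other definition. Taking the any-time definition into the exclusion is therefore the natural reading, though it remains an inference.
3. Section 6.1 already provides for a sparse oedema category: the covariate may be removed from the model. It does not provide for removing children.
4. Section 9.1 now holds both the weight-level and the child-level rule. Once every child with any oedema record is out of the model, the weight-level rule has nothing left to act on there.

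**Size, as an illustration**

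Inputs from the SAP:
- 4 children with oedema (footnote [1]).
- Interim size from Section 3: "An interim analysis was planned when approximately 100 evaluable subjects have completed the study".
- Share affected: 4/100 = 4%.

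Assumptions, because the SAP is silent:
- 50 children per arm at the interim.
- D, the difference in mean weight gain between excluded and retained children, is 5 to 20 g/kg/day and the same in both arms.

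An arm's mean with all children kept equals the retained mean plus (share excluded × D). Hence

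shift in treatment difference = (a − b)/50 × D,

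where a and b are the numbers excluded in the two arms.

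- Split 4:0: 4/50 × 5 = 0.4, up to 4/50 × 20 = 1.6 g/kg/day.
- Split 3:1: 2/50 × 5 = 0.2, up to 2/50 × 20 = 0.8 g/kg/day.
- Split 2:2: 0.

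These figures compare excluding all 4 children with keeping all 4. For the any-time rule against a Day 0 rule, only children whose oedema began after Day 0 count. If none of the 4 did, the two rules remove the same children and the shift is exactly 0. If one did, it is 1/50 × 5 = 0.1 to 1/50 × 20 = 0.4 g/kg/day.

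For scale, the interim Bayesian table in Section 9.1 uses thresholds of 0, 1, 2 and 4 for the difference in rate of weight gain.

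**The case against.** The strongest reply is that this is a disclosed choice in an exploratory study. Section 1.2 warns that the analysis plan may change after the interim, Section 9 permits departures from the ITT population where specified, and Section 9.1 specifies one. The reason given is a sparse category. The plan also clearly expects oedema at entry: it is a Day 0 characteristic, and the baseline weight moves to the first oedema-free record. All 4 children may have had it then.

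Much of this stands. A reader might infer that the exclusion breaches the ITT principle in Section 4, where "The data will be analysed according to the treatment to which the subject was randomised". That sentence concerns the arm in which a child is counted, and the exclusion does not alter it. A reader might also infer that the rule was chosen because of the interim treatment effect. The SAP says only that it followed review of the interim results, and the reason it gives is the count of 4.

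It is also fair to say that omitting single weights is not free of assumptions. That too conditions on a post-randomisation state, and the mixed model then relies on those weights being missing at random although fluid status bears directly on weight.

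What the reply does not meet is that the rule as written applies to every child in the final analysis, whose oedema count is not stated, and that its stated reason justifies a simpler model and not a smaller set of children.

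**Conclusion.** The point holds as a specification flaw that should be repaired. As written, the rule lets post-randomisation records decide who enters the primary weight model, no retaining model is planned, and Section 9.1 carries two rules that need reconciling.

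Its size is uncertain. The effect against a Day 0 rule is zero if all affected children had oedema at entry. If neither late onset nor the weight gain of those children depends on arm, there is no bias on average and the loss is in precision. Otherwise, with 4 children in about 100, the shift is probably small. Even the extreme illustration, all 4 of late onset, in one arm and 20 g/kg/day from the rest, gives 1.6 g/kg/day, and it rests on assumed values throughout. A reader might take such a figure as evidence that the result is biased by that amount. The documents do not support that, because they give neither onset day, nor arm, nor the weight gain of these children. Nor do they bound the effect at zero.

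The conclusion depends on reading the exclusion with the Section 6.1 definition. If the sponsor meant oedema at entry only, the SAP should say so, and most of the concern falls away.

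**What to change.** - In Sections 6.1 and 9.1 and in footnote [1], define the excluded and separately summarised group by oedema at Day 0 only, and name the CRF record that decides it.
- For oedema first recorded later, keep the child and omit only weights taken while oedema was detectable, as Section 9.1 already provides. State that this relies on missing at random.
- Add one sensitivity MMRM in all ITT children, using Section 9.1's existing rules: first oedema-free weight as baseline, and weights during oedema omitted. State how many days the gain is divided by when that baseline falls after Day 0.
- Report exclusions by arm and by day of onset.
- Reconcile the scope: footnote [1] speaks of the statistical analysis in general, Section 9.1 of weight only, and the body of Table 1 still lists oedematous status as a factor.

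The cost is SAP wording and one extra model run. Oedema status is already on the daily monitoring chart, so no new data are needed. The downside is a few intermittently missing weights, which the mixed model can handle under the stated assumption.
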